Funding: No funding to report as of now. Funding by The Research Council of Norway is proposed after evaluation the developed prototype mentioned in this article.

Correspondence concerning this article should be addressed to [name]

IIIT Delhi University, [name].

Email: [contact]

ABSTRACT

Background: To take the existing VR technology to the next level, we developed a novel Intelligent Virtual Reality Therapy System (IVRTS). Aim: The objective of this project had three aspects: Namely, development of the novel IVRTS technology involving the development of a hardware device, development of Artificially Intelligent Psychotherapeutic software-interface and testing it's clinical efficacy. *Methods*: It used a two-phased methodology; Development of the novel technology and testing its Clinical Efficacy. After development of Novel IVRTS. A 7-week intervention was designed for each subject. The sample of 500 patients, meeting the criteria of Acrophobia and Anxiety, underwent the interventions at The GTB hospital (The University of Delhi), for a total 3500 sessions, ranging 5250 hours for over 2 years. The subjects were randomly divided into 4 groups: IVRTS Group, Mindfulness group, CBT group and Control Group. *Registration:* The ethics committee and clinical trial registration number is 3/1/333011/HRD. *Results*: The IVRTS group reported significant reduction in Acrophobic and Anxiety symptoms. The Pre and Post intervention, mean and SD reduced from 28.60±8.45 to 11.10±4.03 on HAMA; from 8.10±1.56 to 3.73±1.23 on SUDS and increased from 72.87±6.21 to 87.07±3.79 on WHO-QOL-BREF. It was also seen the mean comparison of reduction was significantly higher compared to the CBT and Mindfulness Groups. It also indicated enhanced Quality of Life (p < .001) compared to The Mindfulness Group and CBT Group. *Conclusion:* IVRTS decreased symptoms of Acrophobia and Anxiety, enhanced Quality of Life significantly than other treatment groups. Development of this technology is a land-mark innovation.

Key Words: Anxiety; Virtual Reality; Phobias; Treatment Intervention.

INTRODUCTION

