In this health-related research, the researchers first applied to health research ethics committees for permissions and once the permissions are taken, then the researchers identified the sample or user groups, through seminars at the Gjøvik hospital, using social media, etc. The researchers made sure that the user consent is received, the participation in our studies are voluntary and their participation can be ended any time by the user without any penalties for the user. Also, the Clinical Trials took place at The Psychiatry OPD of the Guru Tegh Bahadur Hospital of The University of Delhi.

Figure 4: The software detects the pupil, after detection it determines the focus point of gaze to control the virtual interaction

Hypothesis:

- (i) The new novel developed technology Intelligent Virtual Reality Therapy System (IVRTS) is more effective in reducing symptoms of Phobia and Anxiety as compared to Mindfulness Meditation and Cognitive Behavior Therapy Groups.
- (ii) The novel IVRTS Group scores significantly lower on both Hamilton Anxiety Inventory (HAM-A) and Subjective Units of Dysfunction Scale (SUDS) compared to all three, The Control Group, The Mindfulness Group Cognitive Behavior Therapy (CBT) Group.
- (iii) The Novel IVRTS Group scores significantly higher on WHO Quality of Life Scale (WHO QOL BREF) compared to all three, The Control Group, The Mindfulness Meditation Group and The CBT Group.
- (iv) The new technology proves to be effective and a steppingstone towards a newer era in the treatment of Mental Health issues using Mental healthcare engineering.

Sample

The Clinical Trials were carried out on 500 adults with Acrophobia which is fear of heights co-morbid with Generalized Anxiety. The sample for the study was recruited from the patients/subjects attending the adult psychiatric OPD of the department of Psychiatry GTB Hospital of The University of Delhi and fulfilling the

ICD-10 diagnostic criteria for assessment of Acrophobia and generalized anxiety. The study was conducted on an initial 500 subjects attending the psychiatric OPD of the department of Psychiatry GTB Hospital of the University of Delhi. The subjects were equally and randomly assigned to three groups namely; Novel Intelligent Virtual Reality System (IVRTS) Group (n=125), Mindfulness Meditation Group (n=125), Cognitive Behavior Therapy (CBT) Group (n=125) and The Control Group (n=125).

[figure not shown]

Figure 5: Consort Diagram

Inclusion Criteria

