(CBT) states that it is not the situation itself but the thought associated with the situation (stimulus) which makes an individual fearful. Altering this thought and the emotions related to it is hence helpful in treating phobias. This was achieved by integrating an automated intelligent Cognitive Behavior Therapy software program with the VR device. 4) Finally, the researchers used Mindfulness Relaxation as a treatment for phobia. This was implemented by making the subject face the anxiety-provoking situation with the help of VR equipment and simultaneously working on reducing the anxiety emotions with the help of guided mindfulness meditation accompanied by meditation music, along with the developed automated intelligent therapy software interface. This methodology was intended to put the subject in a peaceful state of mind, detaching them from negative thoughts and fears, working on the principle that anxiety and relaxation cannot coexist.

[figure not shown]

Figure 6: Understanding CBT Software

Project Plan

[figure not shown]

Figure 7: Project plan

01/08/2020

OUTCOMES AND RESULTS

The quantitative and qualitative results were analyzed with the appropriate statistical and analytical tools. Various statistical modalities were used to establish efficacy, efficiency and the frequencies evaluated. Paired sample t- test were conducted in this study to assess the statistical significance of the interventions.

Independent sample t-test and ANOVA were tested in the data. Correlation analysis was also performed, The association between two categorical variables is enumerated by Chi-square test.

Scale	Mindfulness (n=118)		Control (n=125)		t-	F-	p-value
	Pre	Post	Pre	Post	value	value	
	Mean±SD		Mean±SD				
HAMA	32.86±5.76	19.62±4.24	33.70±6.08	28.00±6.49	8.350	2.327	0.000
SUDS	8.24±0.95	5.69±1.04	8.27±1.11	6.03±1.29	1.228	0.178	0.225
QOL	73.86±7.73	84.10±5.19	75.47±5.44	82.53±4.85	-2.229	6.242	0.030

Table 1: Mean comparison between Mindfulness Meditation group (n=118) and control group (n=125)

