Table 1 represents the mean comparison between Mindfulness group and the Control Group of respondents while before and after intervention. On The Hamilton Anxiety scale, most of the respondents in The Mindfulness Group had very severe condition while before intervention with mean score (M=32.86), but it reduced to mean score (M=19.62). While in the control group, most of the respondents had very severe condition while before intervention with mean score (M=33.70) and moderate to severe condition while after intervention with mean score (M=28.00). The obtained t-value and p-value for Hamilton scale are 8.350 and 0.000 respectively. Here, p-value is less than 0.01; it indicates that there is a statistically significant difference between mindfulness and control group of respondents based on Hamilton scale. Similarly when considered the Subjective Unites of Dysfunction Scale (SUDS), most of the respondents of The Mindfulness Group, felt 'Freaking out' while before intervention with mean score (M=8.24) and 'Moderately upset' while after

intervention with mean score (M=5.69). But in the control group, most of the respondents felt 'Freaking out' while before intervention with mean score (M=8.27) and 'bad' while after intervention with mean score (M=6.03). The obtained t-value and p-value for SUDS are 1.228 and 0.225 respectively. Here, p-value is greater than 0.05, and indicated that there is no significant difference between mindfulness and control group of respondents based on SUDS. Similarly, obtained t-value and p-value for Quality of life are -2.229 and 0.030. Here p-value is less than 0.05; and shows a statistically significant difference between Mindfulness and Control group in relation to WHO Quality of life (QOL - BREF) scale of respondents.

	CBT (n=106)		Control (n=125)				
Scale	Pre	Post	Pre	Post	t-	F-	p-
	Mean±SD		Mean±SD		value	value	value
HAMA	32.52±5.24	21.03±4.29	33.70±6.08	28.00±6.49	6.905	2.312	0.000
SUDS	8.24±0.98	5.34±1.14	8.27±1.11	6.03±1.29	2.366	0.344	0.021
QOL	73.62±5.23	83.28±5.06	75.47±5.44	82.53±4.85	-2.714	0.002	0.009

Table 1: Mean comparison between CBT group (n=106) and Control group (n=125)

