Table 3 presents the mean comparison between The Novel Intelligent Virtual Reality Therapy System (IVRTS) and control group of respondents. On the Hamilton Anxiety scale of, most of the respondents of the Novel IVRTS Group had a score representing moderate to severe condition before the intervention with mean (M=28.60), and reduced to mild condition after the intervention with mean (M=11.10). In the control group, most of the respondents were in very severe condition before intervention with mean (M=33.70) and moved to moderate to severe condition after intervention with mean (M=28.00). The obtained t-value and p-value for Hamilton Anxiety scale is 8.088 and 0.000 respectively. Here, p-value is less than 0.01, it indicates that there is a statistically significant difference between The Novel IVRTS Group and The Control Group on Hamilton scale. Similarly, on the SUDS of respondents, most of the respondents of The IVRTS Group felt 'Freaking out' before the intervention (M=8.10) and 'No Significant Distress' after the intervention with mean

(M=3.73). In the control group, most of the respondents felt 'Freaking out' before the intervention with mean (M=8.27) and moved to feeling 'bad' after the intervention with mean with mean (M=6.03). The obtained t-value and p-value for SUDS are 7.503 and 0.000 respectively. Here, p-value is less than 0.01, it indicates that there is a statistically significant difference between The Novel IVRTS Group and The Control group based on SUDS. Similarly, the obtained t-value and p-value for The WHO Quality of life Scale were -6.313 and 0.009. Here p-value is less than 0.01, and indicates a statistically significant difference between The Novel IVRTS and Control group on The WHO Quality of life (QOL-BRF) scale of respondents.

Scale	Mindfulness		CBT		Novel IVRTS		
	Pre	Post	Pre Post		Pre	Post	
	Mean±SD		Mean±SD		Mean±SD		
HAMA	32.86±5.76	19.62±4.24	32.52±5.24	21.03±4.29	28.60±8.45	11.10 ± 4.03	
SUDS	8.24 ± 0.95	5.69 ± 1.04	8.24 ± 0.98	5.34 ± 1.14	8.10 ± 1.56	3.73 ± 1.23	
QOL	73.86±7.73	84.10±5.19	73.62±5.23	83.28±5.06	72.87±6.21	87.07±3.79	

Table 4: Efficacy of Interventions based on the HAMA, SUDS and WHO QOL scale

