Finally Table 4, shows the comparison analysis between the various interventions to show which intervention proved to be the most effective and efficient for the patients. Interventions namely, Mindfulness Meditation, CBT and Novel Intelligent Virtual Reality Therapy System (IVRTS). The mean scores after intervention on both The Hamilton Anxiety Scale and The Subjective Units of Dysfunction Scale for the Novel IVRTS Group is significantly less than the mean scores (HAMA=11.10, SUDS=3.73) of The Mindfulness Group (HAMA=19.62, SUDS=5.69) and the CBT Group (HAMA=21.03, SUDS=5.34). In addition, The Novel IVRTS Group has a higher mean score on The WHO Quality of Life Scale (QOL=87.07) compared to the Mindfulness Group (QOL=84.10) and the CBT Group (QOL=83.28). The p-value is less than 0.01 respectively indicating a significant difference between Novel IVRTS compared to other interventions including CBT, Mindfulness and

Control groups. Considering the all the above comparisons of statistical significance modalities namely, The Mean Scores, Standard Deviations, t-scores and p-scores. The study concludes that, The Novel Intelligent Virtual Reality Therapy System (IVRTS) intervention is the most effective and efficient intervention compared to Mindfulness and even CBT.

Through the various approaches explained henceforth, the researchers aspired to create a more effective, image-based treatment system for phobias, based on the combination of principles of Psychology and Virtual Reality. The treatment methodologies thus aimed to automate the process oftherapy thereby making the process faster and more practical.

Moreover, the new technology is for the first time used to develop human, AI interaction for treatment, using interactive sensors, intelligent automated psychotherapy interface, and VR imagery scenarios.

DISCUSSION AND CONCLUSION

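### The t-values in Tables 1–3 cannot be tests of the post-intervention scores on which the conclusion rests; the variable tested and the n analysed need to be stated

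*Combined protocol and SAP*

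**What the plan says.** The document names two different quantities.

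- **Score, no time point.** Hypothesis (ii): "The novel IVRTS Group scores significantly lower on both Hamilton Anxiety Inventory (HAM-A) and Subjective Units of Dysfunction Scale (SUDS". Hypothesis (iii): "The Novel IVRTS Group scores significantly higher on WHO Quality of Life Scale (WHO QOL BREF) compared to all three".
- **Score after intervention.** The text on Table 4 rests its claim of superiority on "The mean scores after intervention on both The Hamilton Anxiety Scale and The Subjective Units of Dysfunction Scale", followed by the corresponding QOL means and a statement that p is below 0.01.
- **Change.** Hypothesis (i) is about reducing symptoms, and the abstract says "the mean comparison of reduction was significantly higher compared to the CBT and Mindfulness Groups".

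The between-group method is given in one sentence at the start of Outcomes and Results: "Independent sample t-test and ANOVA were tested in the data". It does not say whether post scores or changes were compared. Tables 1–3 (the CBT table is captioned Table 1 but discussed as Table 2) give pre and post mean±SD for each arm and one unlabelled t per scale against Control. Examples from the text are "The obtained t-value and p-value for Hamilton Anxiety scale is 8.088 and 0.000 respectively" (IVRTS) and "Similarly, obtained t-value and p-value for Quality of life are -2.229 and 0.030" (Mindfulness). No SD of change and no between-group difference is printed.

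**The concern.** A reader of the text on Table 4 will attach each p-value to the gap between post means. If the t-values come from another variable, that pairing is wrong. The size of effect and its significance would then describe different things, and some verdicts could differ on the quantity named. It matters most where the arms differed at baseline, because a raw post-score gap counts that imbalance as treatment effect. IVRTS started at 28.60 on HAM-A and Control at 33.70.

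**Working it through.** **Inputs.** Pre and post mean±SD, n and t from Tables 1–3: Mindfulness n=118, CBT n=106, IVRTS n=115, Control n=125. Differences are Control minus intervention, which matches the printed signs.

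**Step 1: try to reproduce the printed t as a post-score test.** Pooled SD: sp² = [(n1−1)s1² + (n2−1)s2²]/(n1+n2−2); t = d / [sp·√(1/n1+1/n2)].

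IVRTS HAM-A: d = 28.00 − 11.10 = 16.90; sp² = (114×4.03² + 124×6.49²)/238 = 29.72, so sp = 5.452; SE = 5.452×√(1/115+1/125) = 0.7045; t = 23.99. Printed: 8.088.

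| vs Control | Scale | Printed t | Post-score t, printed n | Post-score t, 29/30 | Equal n per arm needed |
|---|---|---|---|---|---|
| Mindfulness | HAM-A | 8.350 | 11.84 | 5.85 | 60 |
| | SUDS | 1.228 | 2.25 | 1.11 | 36 |
| | QOL | −2.229 | −2.44 | −1.20 | 102 |
| CBT | HAM-A | 6.905 | 9.44 | 4.85 | 59 |
| | SUDS | 2.366 | 4.27 | 2.17 | 35 |
| | QOL | −2.714 | −1.15 | −0.58 | 643 |
| IVRTS | HAM-A | 8.088 | 23.99 | 11.97 | 13 |
| | SUDS | 7.503 | 14.11 | 7.01 | 34 |
| | QOL | −6.313 | −8.03 | −4.00 | 73 |

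The last column is t²(s1²+s2²)/d². For CBT QOL: 2.714²×(5.06²+4.85²)/0.75² = 643, in a trial of 500. None of the nine is reproduced.

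**Step 2: could another n rescue the post-score reading?** The three scales in a table share the same two arms, so the ratio of two t-values depends only on how patients split between arms. Over all splits, with ±0.01 allowed for rounding of the mean differences:

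- IVRTS HAM-A/SUDS must lie in 1.45–2.25; printed 1.08.
- IVRTS HAM-A/QOL must lie in 2.77–3.51; printed 1.28.
- CBT QOL/SUDS must lie in 0.24–0.30; printed 1.15.
- Mindfulness QOL/SUDS must lie in 0.89–1.27; printed 1.82.

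All nine within-table ratios fall outside their possible range. With each arm searched from 3 to 500, the best single pair still misses at least one row by 20% (Mindfulness), 60% (CBT) and 37% (IVRTS).

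**Step 3: what n do the printed p-values imply?** At 57 df, t = 1.228, 2.229, 2.366 and 2.714 give p = 0.224, 0.030, 0.021 and 0.009, against 0.225, 0.030, 0.021 and 0.009 printed. At the df for the printed n (241 for Mindfulness, 229 for CBT) the last three would be 0.027, 0.019 and 0.007. The p-values therefore point to about 29–30 per arm.

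**Step 4: does change fit?** The SD of change is not given, so I assume one pre-post correlation r per row and solve for it. The variance of change in each arm is s_pre² + s_post² − 2r·s_pre·s_post.

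IVRTS HAM-A: the difference in change is 17.50 − 5.70 = 11.80; SE = 11.80/8.088 = 1.459; at 29/30 the pooled change SD needed is 1.459/√(1/29+1/30) = 5.60, which gives r = 0.71.

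| vs Control | Difference in change (HAM-A / SUDS / QOL) | r needed at 29/30 |
|---|---|---|
| Mindfulness | 7.54 / 0.31 / −3.18 | 0.83 / 0.62 / 0.60 |
| CBT | 5.79 / 0.66 / −2.60 | 0.84 / 0.56 / 0.75 |
| IVRTS | 11.80 / 2.13 / −7.14 | 0.71 / 0.67 / 0.68 |

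At the printed n, r would have to run from −0.82 to 0.37 and be negative in 6 of 9 rows. Two other readings also fail: the baseline scores do not give the printed t-values, and an ANCOVA at 29/30 gives at least 10.9 for IVRTS HAM-A over the r values tried.

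**Step 5: do verdicts change on the post score?**

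| vs Control | Printed p | Post-score p, printed n | Post-score p, 29/30 |
|---|---|---|---|
| CBT QOL | 0.009 | 0.25 | 0.56 |
| Mindfulness SUDS | 0.225 | 0.025 | 0.27 |
| Mindfulness QOL | 0.030 | 0.016 | 0.24 |
| IVRTS, all three | 0.000 in Table 3 | <0.001 | <0.001 |

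For IVRTS HAM-A the post gap splits exactly: 16.90 = 11.80 (difference in change) + 5.10 (33.70 − 28.60 at baseline).

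**The case against.** The strongest reply is that the document may have meant change all along. Hypothesis (i) and the abstract name reduction, hypotheses (ii) and (iii) give no time point, and the text on Tables 1–3 sets pre and post means beside each t. That stands as far as it goes. The wording is ambiguous, and only the text on Table 4 clearly names post means. A reader might infer that hypotheses (ii) and (iii) have no reported test at all; for IVRTS against Control the documents do not support that.

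A reader might also take it as established that change scores were tested. They were not shown to be. With no change SDs printed, each row has its own free correlation, so nine parameters fit nine t-values. Sixty per arm also fits, with r from about 0.1 to 0.67. The change reading gains weight only from its agreement with the df in the p-values, and that same agreement contradicts the printed n.

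Nor does HAM-A alone exclude post scores. With a pooled variance, Control 30 with Mindfulness 102, CBT 103 and IVRTS 11 gives 8.35, 6.91 and 8.05, within 0.5% of print. The exclusion comes from comparing scales within a table.

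Finally, 16.90 and 11.80 are subtractions from the tables, not effect sizes that the authors state.

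**Conclusion.** The concern holds in this form: the t-values in Tables 1–3 are not post-score tests at the printed n or at any single pair of arm sizes up to 500 per table, yet the text on Table 4 rests significance on post means. That conclusion uses only the printed means, SDs and t-values and the assumption that a table's three scales share the same patients. That the tests were on change is a plausible inference, conditional on about 29–30 per arm and r of 0.56–0.84. At the printed n, the post-score reading fails and the change reading needs mostly negative correlations, so n, t and p disagree whichever is meant.

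The comparison of IVRTS with Control is not overturned; what changes there is the size of effect a reader should take from HAM-A. The QOL claim for CBT against Control is not supported on the post score at either n. The Mindfulness SUDS and QOL verdicts depend on which n is real.

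**What to change.** 1. From the data files, establish and state which variable was tested and how many patients per arm were analysed.
2. Re-run all nine comparisons against Control on the post score adjusted for baseline (ANCOVA). Alternatively, label the existing t-values as tests of change, if the files confirm it.
3. In Tables 1–3 add mean change ± SD per arm and the between-group difference with its 95% CI. Compute the intervals from the data; they cannot be derived reliably from the printed t-values while n is unresolved.
4. Base the text on Tables 1–4 on that one quantity, and do not pair p-values from one variable with means of another.
5. Leave hypotheses (ii) and (iii) as worded. Rewriting them around observed differences would fit the hypotheses to the results.

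The cost is a re-run on existing data, some relabelling and extra table columns. The HAM-A effect shown for IVRTS will probably be smaller: for an adjustment slope between 0 and 1, the ANCOVA difference lies between 16.90 and 11.80. The QOL claims for CBT and Mindfulness may weaken.

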Table 2 presents the mean comparison between CBT group and control group of respondents before and after intervention. On the Hamilton Anxiety scale, most of the respondents of the CBT Group had very severe condition while before intervention with mean score (M=32.52), which reduced to mild to moderate severe after the intervention witj mean score (M=21.03). In control group, most of the respondents were in very severe condition while before intervention with mean score (M=33.70) and improved to moderate to severe condition after the intervention with mean (M=28.00). The obtained t-value and p-value for Hamilton scale are 6.905 and 0.000 respectively. Here, p-value is less than 0.01, it indicates a statistically significant difference between CBT and control group of respondents based on Hamilton Anxiety scale. Similarly, on the SUDS of respondents, most of the respondents felt 'Freaking out' while before intervention with mean (M=8.24) and

'Moderately upset' after the intervention with mean (M=5.34). But in the control group, most of the respondents felt 'Freaking out' before the intervention with mean (M=8.27) and felt 'bad' after intervention with mean (M=6.03). The obtained t-value and p-value for SUDS is 2.366 and 0.021 respectively. Here, p-value is less than 0.05, indicating a statistically significant difference between CBT and control group of respondents based on SUDS. Similarly obtained t-value and p-value for Quality of life are -2.714 and 0.009. Here p-value is less than 0.01; indicating a statistically significant difference between CBT and Control group in relation to The WHO Quality of life (QOL- BREF) scale of respondents.

	Novel IVRTS (n=115)		Control (n=125)		t-	F-	
Scale	Pre	Post	Pre	Post	_		p- value
	Mean±SD		Mean±SD		value	value	value
HAMA	28.60±8.45	11.10±4.03	33.70 ± 6.08	28.00±6.49	8.088	23.503	0.000
SUDS	8.10±1.56	3.73 ± 1.23	8.27±1.11	6.03 ± 1.29	7.503	2.315	0.000
QOL	72.87±6.21	87.07±3.79	75.47±5.44	82.53±4.85	-6.313	4.519	0.000

Table 3: Mean comparison between IVRTS (n=115) and Control group (n=125)

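### Baseline HAM-A in the IVRTS arm is hard to reconcile with random assignment at the printed group sizes, and the documents do not show whether the assignment or the figures are at fault

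*Combined protocol and SAP*

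**What the plan says.** The Abstract reports that "The subjects were randomly divided into 4 groups: IVRTS Group, Mindfulness group, CBT group and Control Group". The Sample section says "The study was conducted on an initial 500 subjects attending the psychiatric OPD" and that "The subjects were equally and randomly assigned to three groups namely", although it goes on to name four arms of 125 each. The readable text gives no randomisation method, no baseline comparison and no reasons for loss.

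Group sizes come from the table captions: "Table 1: Mean comparison between Mindfulness Meditation group (n=118) and control group (n=125"), "Table 1: Mean comparison between CBT group (n=106) and Control group (n=125") and "Table 3: Mean comparison between IVRTS (n=115) and Control group (n=125"). The CBT table is captioned Table 1 but discussed as Table 2. The Abstract gives the IVRTS result as "mean and SD reduced from 28.60±8.45 to 11.10±4.03 on HAMA".

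The text on Table 3 says most respondents of the "Novel IVRTS Group had a score representing moderate to severe condition before the intervention with mean (M=28.60"), and places Control at the same time point in the very severe class. The text on Table 4 compares post-intervention means without baseline adjustment and ranks IVRTS first.

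**The concern.** Three arms start within 1.2 HAM-A points of each other (32.52 to 33.70). IVRTS alone starts 3.9 to 5.1 points lower, with a wider spread (SD 8.45 against 5.24 to 6.08). Under random assignment of 125 per arm, baseline means should differ only by sampling error, which at these SDs is under one point for a difference between two arms.

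Hypotheses (i) to (iii) and the conclusion that IVRTS outperforms the other arms depend on the arms being comparable apart from treatment. HAM-A is the first outcome reported, and the imbalance lowers the IVRTS post score in any unadjusted comparison. If assignment was not random, adjusting for HAM-A removes only the measured difference. If the group sizes are wrong, every precision statement based on 500 patients is wrong too.

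**Working it through.** **Inputs** (tables under Outcomes and Results; losses are 125 minus the caption n)

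| Arm | n | Lost | HAM-A pre | SUDS pre | QOL pre |
|---|---|---|---|---|---|
| IVRTS | 115 | 10 | 28.60±8.45 | 8.10±1.56 | 72.87±6.21 |
| Mindfulness | 118 | 7 | 32.86±5.76 | 8.24±0.95 | 73.86±7.73 |
| CBT | 106 | 19 | 32.52±5.24 | 8.24±0.98 | 73.62±5.23 |
| Control | 125 | 0 | 33.70±6.08 | 8.27±1.11 | 75.47±5.44 |

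**1. The plan's own figure.** No baseline test is printed. The nearest figure is the Table 3 HAM-A t of 8.088.
- Post scores at n=115 and 125: pooled SD 5.45, SE = 5.45 × √(1/115 + 1/125) = 0.704, t = 16.90/0.704 = 24.0.
- Baseline scores give t = 5.4.
- Change scores (17.50 − 5.70 = 11.80) give 8.09 only if the pre-post correlation is about −0.60 in both arms.
- At 30 per arm, change scores give 8.09 with a correlation of about 0.70, which is ordinary.

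So 8.088 is not reproduced at the printed n in any plausible way.

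**2. Baseline HAM-A at the printed n.**
- The grand mean is 31.95. Between-arm mean square = 1805.6/3 = 601.9; within-arm = 19488.5/460 = 42.37. F = 601.9/42.37 = 14.2, p = 7e-9. Allowing unequal variances (Welch), p = 4e-6.
- IVRTS vs Control: SE = √(8.45²/115 + 6.08²/125) = 0.957; t = −5.10/0.957 = −5.33, p = 3e-7. Against Mindfulness p = 1e-5; against CBT p = 4e-5 (all Welch).
- The other three arms alone: F = 1.32, p = 0.27.
- With 125 in every arm, F = 15.2, p = 2e-9. It therefore makes no difference whether the pre means cover completers or everyone assigned.

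**3. Can dropout explain it?** Control lost nobody, so 33.70 is fixed.
- Mean needed in the 10 missing IVRTS patients to match Control: (125 × 33.70 − 115 × 28.60)/10 = 92.4.
- The documents do not give the scale maximum, so I set all 10 missing to one assumed value and retested against Control: p = 2e-5 at 40, 0.0002 at 45, 0.001 at 50, 0.011 at 56. It reaches 0.05 only at about 62.
- The argument is firmest against Control. CBT lost 19, and its full-arm mean would equal 28.60 if those 19 averaged (125 × 28.60 − 106 × 32.52)/19 = 6.7.

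**4. What the printed p-values say about n.** Two-sided p for each printed t:

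| Printed t | Printed p | p at 57 df | p at caption df |
|---|---|---|---|
| 1.228 (Mindfulness, SUDS) | 0.225 | 0.2245 | 0.221 (241 df) |
| 2.229 (Mindfulness, QOL) | 0.030 | 0.0298 | 0.027 (241 df) |
| 2.366 (CBT, SUDS) | 0.021 | 0.0214 | 0.019 (229 df) |
| 2.714 (CBT, QOL) | 0.009 | 0.0088 | 0.007 (229 df) |

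All four fit about 57 df, which is about 30 per arm. None fits the captions.

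**5. Baseline HAM-A at about 30 per arm** (30 IVRTS and Control, 29 Mindfulness and CBT). F = 153.9/42.46 = 3.63, p = 0.015; Welch p = 0.068. Pairwise Welch p is 0.010 (Control), 0.027 (Mindfulness) and 0.037 (CBT). Variance ratios for IVRTS against the others remain 1.9 to 2.6, but their p-values rise from below 0.001 at the printed n to between 0.013 and 0.08.

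**6. The other two scales.** SUDS means are balanced (four-arm p = 0.69 at printed n), though the IVRTS spread is again the widest. QOL differs at printed n (p = 0.012), with IVRTS lowest; at about 30 per arm p = 0.43. The hypotheses treat higher QOL as better, so on this scale IVRTS starts worst.

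**The case against.** The strongest reply is that the tiny p-values use group sizes that the plan's own test results contradict. At about 30 per arm, with unequal variances allowed for, the four-arm test does not reach 0.05, and the outlying arm and scale were picked out after looking at three scales. This stands. It means the baseline figures alone do not prove faulty assignment. It does not rescue the text, because the captions and the description of a 500-patient randomised comparison would then be wrong.

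A reader might infer that milder patients were steered to the device, or that their baseline was rated after treatment began. The documents do not support either. SUDS means are balanced, and IVRTS has the lowest baseline QOL. The Procedure section says the scales were completed at baseline and repeated after seven sessions. The severity wording for IVRTS adds nothing independent: the same class is applied to Control's post mean of 28.00, so it only restates the number.

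A reader might also infer that the baseline gap accounts for the IVRTS result. It does not do so alone: the printed falls are 17.5 points for IVRTS and 5.7 for Control, against a baseline gap of 5.1.

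The CONSORT diagram (Figure 5) is not available to read. It may explain allocation and losses, but it cannot change the arithmetic in step 3.

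**Conclusion.** The concern holds as an inconsistency. Random assignment of 125 per arm and the printed baseline HAM-A figures cannot easily both be right (p = 7e-9, Welch 4e-6, at the printed n), and loss of 10 IVRTS patients does not explain the gap to Control. Either the assignment or the timing of baseline was not as described, or the printed n or summary figures are wrong. The documents do not show which.

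If the tests were run on about 30 per arm, as the four t and p pairs indicate, the imbalance is suggestive only (p = 0.015, Welch 0.068) and chance remains a fair explanation. The stronger conclusion, that patients were selectively allocated, is not established. The result assumes that the printed means and SDs are correct and that Control's 125 is a true count with no losses. In either case the randomised comparison of 500 patients is not supported as written.

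**What to change.** 1. State the n behind every mean and every test, and reconcile it with the printed t and p values.
2. Check the allocation list against the dates of baseline and first session. Report the randomisation method, and baseline HAM-A, SUDS and QOL for all patients in the arm to which they were assigned.
3. Analyse patients as assigned, with post scores adjusted for the baseline value of the same scale. Flag any baseline taken after the first session and examine it in a sensitivity analysis. A late baseline does not undo randomisation, but it can contaminate the covariate. Patients treated off-list should stay in their assigned arm, since removing them would be a post-assignment exclusion.
4. Keep the description of random assignment only if the allocation list supports it. Otherwise call the IVRTS contrasts non-randomised in the Abstract, the Sample section and the text on Table 4. Until these points are reconciled, do not rank IVRTS first on the present unadjusted comparison.

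The cost is a check of existing records, one baseline table, a re-analysis and some rewording. The downside is a possibly weaker claim.
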